7.6. Data Handling & Transformation

ACQ scores will be calculated under the ACQ-6 variant of the form. The score will be derived by taking the mean average of the 6 values provided (note that whilst FEV is recorded this will not formulate part of the overall score).

Viral loads below the limit of quantification will be treated as zero. Viral load data will be transformed using base 10 logarithm. To account for zero values, one will be added to each viral load measurement before being transformed.

Soluble mediators which generate a detectable signal but are below the lower limit of detection will have an assumed value of half the lower limit of detection; those for which no signal was detected will have an assumed value of zero. Soluble mediators which are above the upper limit of detection will have an assumed value of the highest reading of all the samples on the same assay performed at that time. Normal transformation and/or sensitivity analyses may be performed as necessary depending on the data and the extent of values above and below limits of detection.

AUC values for exploratory analyses will be calculated using the linear trapezoidal method. Missing values will be extrapolated where required.

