7.3.2. Secondary Mechanistic Analysis

Soluble Mediators:

A total of 32 mediators in nasal samples (taken at day -21, 0, 2, 3, 4, 5, 7, 10) and bronchoscopic samples (taken at day -8, day 5) will be measured for each subject.

Values of soluble mediators obtained from bronchial samples will be presented using summary statistics per treatment group and visit. An additional table will summarise per treatment group (for each mediator) the difference in values between mediators taken at D-8 and D5. Analysis to investigate any difference in effect of OC459 and placebo for each mediator will be performed using the difference in values via unpaired (two-sample) t-test or Mann-Whitney U tests for non-parametric data.

Values of soluble mediators obtained from nasal samples will be presented using summary statistics per treatment group and visit. An additional table will summarize per treatment group (for each mediator) the difference between D-21 and peak value (the highest value measured between D0 and D10).

Taking the difference between D-21 and peak value, analysis to determine the difference in effect of OC459 and placebo for each mediator will be performed using unpaired (two-sample) t-test or Mann-Whitney U tests for non-parametric data.

Differences will be considered significant at $P < 0.05$ within a hierarchy of the primary outcome, and interpreted more cautiously for secondary efficacy outcomes, (likewise more so for exploratory outcomes). All P values are two-sided.

Leukocyte numbers:

Values of leukocyte numbers obtained from bronchial samples / flow cytometry will be presented using summary statistics per treatment group and visit. An additional table will summarise per treatment group (for each cell type) the difference in values between samples taken at D-8 and D5. Analysis to investigate any difference in effect of OC459 and placebo for each cell type will be performed using the difference in values via unpaired (two-sample) t-test or Mann-Whitney U tests for non-parametric data.

Eosinophil counts:

Values of blood and sputum eosinophilia will be presented using summary statistics per treatment group and visit. Analysis to investigate any difference in effect of OC459 and placebo for blood and sputum eosinophilia will be performed using the difference in values via unpaired (two-sample) t-test or Mann-Whitney U tests for non-parametric data.

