7.4.4. Further Testing For Outcome Variables

In addition to the above exploratory tests, secondary outcome variables will be measured and analysed using alternative methods if deemed appropriate. Table 03 below contains a table showing the possible comparisons used:

Table 03: Potential Exploratory Analyses of Outcome Variables

Variable:	Comparison				
	Peak during infection (day 0 to 10)	Change from day 0 to peak infection	Area under curve during infection (day 0 to 10)	Total during infection (day 0 to 14)	Average value at each timepoint day 0 to 10
Lower respiratory symptom score ¹	X	X	N/A	X (primary outcome)	X
Upper respiratory symptom score ¹	X	X	N/A	X (secondary outcome)	X
Morning PEFR ²	X (peak fall)	X (secondary outcome)	X	N/A	X
Morning FEV ₁ ²	X (peak fall)	X (secondary outcome)	X	N/A	X
Clinic FEV ₁ ²	X (peak fall)	X (secondary outcome)	X	N/A	X
ACQ-6	(day 10)	X (secondary outcome)	N/A	N/A	N/A
PC ₂₀	(day 7)	X (secondary outcome)	N/A	N/A	(day -9 only)
FeNO	X	X (secondary outcome)	X	N/A	X
Blood eosinophils	X	X (secondary outcome)	N/A	N/A	X
Virus load	X (secondary outcome)	N/A	X	N/A	X
Soluble mediators - nasal ³	X	X (secondary mechanistic outcome)	X	N/A	X
Soluble mediators - bronchial ³	(day 5)	X (secondary mechanistic outcome)	N/A	N/A	(day -8 only)

Items marked as 'X' or with a specific study day are to be assessed as exploratory analyses

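### SAP 7.6 can give an over-range mediator reading a run-dependent value below the upper limit, so an over-range peak can rank below an in-range one

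*SAP*

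**What the plan says.** SAP 7.6 sets the laboratory rules. At the low end, a detectable signal under the lower limit becomes half that limit, and no signal becomes zero. At the high end, soluble mediators "above the upper limit of detection will have an assumed value of the highest reading of all the samples on the same assay". The comparison set is confined to one occasion: "the same assay performed at that time". The section does not say whether *highest reading* includes readings extrapolated beyond the limit. It sets no floor at the upper limit, and it gives neither the number of runs nor how samples are allocated to them. It then adds: "Normal transformation and/or sensitivity analyses may be performed as necessary depending on the data and the extent of values above and below limits of detection".

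The values feed SAP 7.3.2. For each nasal mediator the quantity summarised is "the difference between D-21 and peak value (the highest value measured between D0 and D10"). The arms are compared on it by unpaired t-test or Mann-Whitney U: "Taking the difference between D-21 and peak value, analysis to determine the difference in effect of OC459 and placebo for each mediator". Bronchial mediators are compared on the D-8 to D5 difference. Mediator values also enter the Spearman correlations (SAP 7.3.3) and the exploratory comparisons in Table 03 (SAP 7.4.4), where the nasal and bronchial changes are labelled secondary mechanistic outcomes.

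**The concern.** A sample above the upper limit is known to be at least as high as that limit. A substitute value should not fall below it and should not depend on which other samples were assayed alongside. The upper rule guarantees neither, whereas the rule for detectable low readings is tied to the assay's own limit.

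The nasal endpoint takes each subject's highest value from D0 to D10, which is where over-range readings are most likely to be picked up. If over-range peaks are pulled down by different amounts in different runs, their order against in-range peaks can change. A rank test gives no protection, because the ranks themselves move, and a t-test would use values that are too low. What is at stake is some loss of sensitivity in the mediator comparisons that are meant to show how OC459 works.

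**Working it through.** **Inputs from the documents.** The SAP gives no figure for this rule, so there is none to reproduce. The mediator count in SAP 6.3.2 agrees with SAP 7.3.2: 1+3+2+4+7+4+3+2+6 = 32. There are 8 nasal sampling days and 15 evaluable subjects per arm (SAP 4.4), so 30 × 8 = 240 nasal samples per mediator. Tests are two-sided at 0.05. The number of runs, the limits and the share of readings over range are not given and are assumed below.

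**Step 1: what each meaning implies.** Let U be the upper limit, common to all runs.
- *Highest quantified reading, one run:* the over-range sample ties with the highest in-range reading. No in-range peak ranks above it.
- *Highest quantified reading, several runs:* the substitute is at or below U and differs by run. Reversals against in-range peaks from other runs are possible.
- *Extrapolated readings count:* the substitute is not below U. No over-range peak falls below an in-range peak; only the order among over-range samples is affected.

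**Step 2: an example (assumed values).** U = 1000. Run A's highest in-range reading is 600, so a sample truly above 1000 becomes 600. An in-range sample in run B reads 900. The truly higher sample now ranks lower: 600 < 900. With every over-range reading set to 1000, the order is right.

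**Step 3: simulation.** Assumptions: 600 trials per setting; 15 per arm; log-normal mediator with between-subject SD 0.8 and within-subject SD 0.7 on the log scale; OC459 cuts the infection-related rise by 60%; one common limit; subjects spread at random over 1, 3 or 6 runs; *highest reading* taken as the highest in-range reading. Power is for Mann-Whitney on peak minus D-21. Reversed pairs are over-range peaks ranked below in-range peaks.

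| Runs | Readings over range | Pairs reversed | Mean shortfall below U | Power, no limit | Power, common cap at U | Power, SAP rule |
|---|---|---|---|---|---|---|
| 1 | 2% | 0% | 2.1% | 0.507 | 0.510 | 0.512 |
| 1 | 5% | 0% | 0.2% | 0.532 | 0.512 | 0.510 |
| 1 | 10% | 0% | 0.3% | 0.540 | 0.437 | 0.437 |
| 1 | 20% | 0% | 0.3% | 0.525 | 0.263 | 0.263 |
| 3 | 2% | 3.4% | 11.6% | 0.513 | 0.490 | 0.485 |
| 3 | 5% | 3.3% | 7.0% | 0.517 | 0.482 | 0.470 |
| 3 | 10% | 3.1% | 4.8% | 0.540 | 0.428 | 0.422 |
| 3 | 20% | 3.2% | 3.4% | 0.563 | 0.283 | 0.272 |
| 6 | 2% | 6.8% | 17.3% | 0.537 | 0.530 | 0.502 |
| 6 | 5% | 7.0% | 12.8% | 0.513 | 0.490 | 0.465 |
| 6 | 10% | 6.9% | 9.6% | 0.522 | 0.425 | 0.377 |
| 6 | 20% | 7.6% | 7.4% | 0.593 | 0.300 | 0.258 |

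Common cap minus SAP rule is about 0 points with one run, 0.5 to 1.2 with three and 2.5 to 4.8 with six. Each power has a simulation standard error of about √(0.5 × 0.5 / 600) = 2 points, though all three were computed on the same simulated data.

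**Step 4: how much is due to the rule.** At six runs and 10% over range, the total loss is 0.522 − 0.377 = 0.145. Of this, 0.522 − 0.425 = 0.097 comes from the limit itself, which any cap shares, and 0.425 − 0.377 = 0.048 from the rule. At 20% the split is 0.293 and 0.042.

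**Step 5: other assumptions.** With 5 runs and a 1.05 SD effect, power under the SAP rule against a common cap was 75% v 76%, 75% v 77% and 69% v 74% when 20%, 30% and 50% of placebo peaks were over range. The 1.05 is borrowed from the symptom score (22.21/21.15); the documents give no mediator effect.

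**Step 6: the change actually tested.** A cap does not settle the order of peak minus D-21. With U = 1000, an over-range subject with D-21 of 400 scores 1000 − 400 = 600. An in-range subject with peak 800 and D-21 of 50 scores 750. If the first subject's true peak exceeds 750 + 400 = 1150, that order is wrong even under the cap. In a further simulation (15 per arm, 6 runs, 30% over range), wrong orderings on the change fell from 18.5% under the SAP rule to 10.3% under the cap. In another (5 runs, 10% to 50% over range) they were 14% to 29% against 6% to 23%.

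**The case against.** The wording refers to the highest reading of all samples, not the highest quantified one, and the same paragraph recognises signals outside the limits at the low end. On that reading the substitute is not below the limit. All that is disturbed is the order among over-range samples, which the proposed cap discards as well. Frozen storage pending analysis (Protocol 9.11) is compatible with a single batch, and one run gives no reversals. SAP 7.6 also foresees sensitivity analyses, and SAP 7.3.2 asks for more cautious interpretation beyond the primary outcome.

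Most of this stands as a limit on the claim. It does not remove it. The SAP does not choose between the two meanings, and limiting the comparison to one assay occasion makes more than one run plausible without establishing it. The sensitivity analyses are optional, have no stated trigger or method, and leave the main rule as it is.

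A reader might infer that the peaks *are* mis-ranked and a true OC459 effect materially diluted. The documents do not support that: it needs several runs, over-range readings and the quantified-reading meaning, and none of these is stated. One 5-run simulation found that 54% to 58% of over-range peaks fell below at least one in-range peak. That figure counts a single reversal per peak; by pairs the share is about 3% to 8% with three to six runs. A reader might also infer that capping makes over-range subjects tie at the top. That is true of the peaks but not of the tested change (Step 6).

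**Conclusion.** The point holds conditionally. The upper-limit rule has no floor and is specific to the assay occasion. Under the quantified-reading meaning it can assign a value below what the sample is known to exceed, and with several runs it can rank an over-range peak below an in-range one. Under the extrapolated meaning, with a common limit, only the order among over-range samples suffers.

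The mechanism follows from the wording; the size does not. Under the assumed inputs the extra power loss against a common cap is about 0 to 5 points, near zero with one run. When 10% to 20% of readings are over range, most of the loss comes from the assay limit itself. Only secondary mechanistic and exploratory mediator analyses are affected. The primary symptom score is untouched. This merits a correction because a clearer and better rule costs almost nothing, not because the trial's main conclusion depends on it.

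**What to change.** In SAP 7.6, replace the upper-limit rule: every over-range reading of a mediator takes one common value, equal to that mediator's upper limit of detection, or the highest upper limit across runs if limits differ. In SAP 7.3.2, specify the Mann-Whitney test for any mediator with over-range peaks. Report the number of over-range readings by arm and run.

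This removes reversals of the peaks by construction. It reduces mis-ordering on peak minus D-21 but does not eliminate it, and the SAP should not claim otherwise. The cost is a sentence or two, an added count in the mediator tables and no new samples. The small downside is that over-range readings become ties, so any order among them is lost.

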7.7. Software of Analysis

Statistical analysis of primary and secondary endpoints will be performed using SAS 9.4. Additional graphical output may be performed using R.

APPENDIX A – INDEX OF TABLES, FIGURES & LISTINGS

Baseline Variables

- Table 1.01 – Summary of Demographic Baseline Variables**
- Table 1.02 – Summary of Demographic Variables at Randomisation (Day -21)**
- Table 1.03 – Summary of Demographic Variables at Inoculation (Day 0)**

Primary Analysis

- Table 2.01 – Listing of Lower Respiratory System Scores**
- Table 2.02 – Summary of Uncorrected Total Lower Respiratory System Scores**
- Table 2.03 – Mann-Whitney U Test of Total Lower Respiratory System Scores**
- Figure 2.04 – Box & Whisker Plot of Total Lower Respiratory System Scores**
- Figure 2.05 – Box & Whisker Plot of Daily Lower Respiratory System Scores**

Secondary Efficacy Analysis

- Table 3.01 – Summary of Corrected Total Lower Respiratory System Scores**
- Table 3.02 – Mann-Whitney U Test of Corrected Lower Respiratory System Scores**
- Table 3.03 – Summary of Total Upper Respiratory System Scores**
- Table 3.04 – Mann-Whitney U Test of Total Upper Respiratory System Scores**
- Table 3.05 – Summary of Effect of Treatment on Asthma Exacerbation Variables**
- Table 3.06 – Statistical Testing on Effect of Treatment on Asthma Exacerbation Variables**
- Table 3.07 – Summary of Effect of Treatment on Viral Load Results**
- Table 3.08 – Statistical Testing on Effect of Treatment Viral Load Results**

Secondary Mechanistic Analysis

- Table 3.09 - Summary of Nasal Soluble Mediators per visit**
- Table 3.10 - Summary of Change from Baseline to Peak Value for Nasal Soluble Mediators**
- Table 3.11 - Statistical Testing of Nasal Soluble Mediators**
- Table 3.12 - Summary of Bronchial Soluble Mediators per visit (D-8, D5)**
- Table 3.13 - Summary of Change from Baseline (D-8) to Infection (D5) for Bronchial Soluble Mediators**

- Table 3.14 - Statistical Testing of Bronchial Soluble Mediators**
- Table 3.15 - Summary of Leukocyte Numbers per visit (D-8, D+5)**
- Table 3.16 - Summary of Change from Baseline (D-8) to Infection (D+5) for Leukocyte Numbers**
- Table 3.17 - Statistical Testing of Leukocyte Numbers**
- Table 3.18 - Summary of Blood and Sputum Eosinophilia**
- Table 3.19 - Summary of Change from Baseline to Peak Value for Blood and Sputum Eosinophilia**
- Table 3.20 - Statistical Testing for Blood and Sputum Eosinophilia**

Secondary Analysis – Correlation Testing

- Table 3.21 - Spearmans Rank Correlation Testing**
- Figure 3.22 - Correlation output**

Secondary Safety Analysis

- Table 3.23 - Summary of Adverse Events by Treatment and Timepoint**
- Table 3.24 - Summary of Adverse Events by Treatment and Severity**
- Table 3.25 - Summary of Adverse Events by Treatment and Relationship to Study Treatment**
- Table 3.26 - Listing of Serious Adverse Events**
- Table 3.27 - Summary of Serious Adverse Events by Treatment and Timepoint**
- Table 3.28 - Summary of Serious Adverse Events by Treatment and Severity**
- Table 3.29 - Summary of Serious Adverse Events by Treatment and Relationship to Study Treatment**
- Table 3.30 - Summary of Vital Signs Results**
- Table 3.31 - Summary of Clinical Chemistry & Haematology Results**

Exploratory Analysis

- Table 4.xx - Exploratory Analyses (as required)**

APPENDIX B – SHELL TABLES, FIGURES & LISTINGS

Baseline Variables

Table 1.01 – Summary of Demographic Baseline Variables

Variable*	Statistics	OC459 (N = xx)	Placebo (N = xx)
Age (y)	N		
	Mean		
	SD		
	Min		
	Median		
	Max		

*Variables for inclusion as per section 6.1

Table 1.02 – Summary of Demographic Variables at Randomisation (Day -21)

See Table 1.01

Table 1.03 – Summary of Demographic Variables at Innoculation (Day 0)

See Table 1.01

Primary Analysis

Table 2.01 – Listing of Lower Respiratory System Scores

		Visit Scores															
Treatment	Subject	D0	D1	D2	D3	D4	D5	D6	D7	D8	D9	D10	D11	D12	D13	D14	Total

Table 2.02 – Summary of Uncorrected Total Lower Respiratory System Scores

Treatment	Visit	n	Mean	SD	Median	Min.	Max.	IQR
OC459	D0							
	...							
	D14							
	Total							
Placebo	D0							
	...							
	D14							
	Total							

Table 2.03 – Mann-Whitney U Test of Total Lower Respiratory System Scores

Median Scores (Number of Points Above Median) for Variable Response Classified by Variable Treatment					
Treatment	N	Sum of Scores	Expected Under H0	Std Dev Under H0	Mean Score
Active	XX	XX	XX	XX	XX
Placebo	XX	XX	XX	XX	XX

Average scores were used for ties.

Two-Sample Test	
Statistic (S)	XX
Normal Approximation	
Z	XX
One-Sided Pr > Z	XX
Two-Sided Pr > Z	XX
t Approximation	
One-Sided Pr > Z	XX
Two-Sided Pr > Z	XX
Exact Test	
One-Sided Pr >= S	XX
Two-Sided Pr >= S - Mean	XX

Figure 2.04 – Box & Whisker Plot of Total Lower Respiratory System Scores

[figure not shown]
[figure not shown]

Figure 2.05 – Box & Whisker Plot of Daily Lower Respiratory System Scores

Secondary Efficacy Analysis

Table 3.01 – Summary of Corrected Total Lower Respiratory System Scores

See Table 2.02

Table 3.02 – Mann-Whitney U Test of Corrected Lower Respiratory System Scores

See Table 2.03

Table 3.03 – Summary of Total Upper Respiratory System Scores

See Table 2.02

Table 3.04 – Mann-Whitney U Test of Total Upper Respiratory System Scores

See Table 2.03

Table 3.05 – Summary of Effect of Treatment on Asthma Exacerbation Variables

Laboratory Test (units)*	Treatment	Visit	n	Mean	SD	Median	Min.	Max.	IQR
xxxxx (xxxx)	Control								
	Treatment								

*Variables for inclusion as per section 6.3.1

Table 3.06 – Statistical Testing on Effect of Treatment on Asthma Exacerbation Variables

For normally distributed data variables:

Source	DF	Sum of Squares	Mean Square	F Value	Pf > F
Model	XX	XX	XX	XX	XX
Error	XX	XX	XX		
Corrected Total	XX	XX			

For non-parametric data variables: See Table 2.03

Table 3.07 – Summary of Effect of Treatment on Viral Load Results

Laboratory Test (units)*	Treatment	Visit	n	Mean	SD	Median	Min.	Max.	IQR
xxxxx (xxxx)	Control								
	Treatment								

*Variables for inclusion as per section 6.3.1

Table 3.08 – Statistical Testing on Effect of Treatment Viral Load Results

For normally distributed data variables:

Source	DF	Sum of Squares	Mean Square	F Value	Pf > F
Model	XX	XX	XX	XX	XX
Error	XX	XX	XX		
Corrected Total	XX	XX			

For non-parametric data variables: See Table 2.03

Secondary Mechanistic Analysis

Table 3.09 - Summary of Nasal Soluble Mediators per visit

Laboratory Test (units)*	Treatment	Visit	n	Mean	SD	Median	Min.	Max.	IQR
xxxxx (xxxx)	Control								
	Treatment								

Table 3.10 - Summary of Change from Baseline to Peak Value for Nasal Soluble Mediators

See Table 3.09

Table 3.11 - Statistical Testing of Nasal Soluble Mediators

For normally distributed data variables:

Source	DF	Sum of Squares	Mean Square	F Value	Pf > F
Model	xx	xx	xx	xx	xx
Error	xx	xx	xx		
Corrected Total	xx	xx			

For non-parametric data variables: See Table 2.03

Table 3.12 - Summary of Bronchial Soluble Mediators per visit (D-8, D5)

See Table 3.09

Table 3.13 - Summary of Change from Baseline (D-8) to Infection (D5) for Bronchial Soluble Mediators

See Table 3.09

Table 3.14 - Statistical Testing of Bronchial Soluble Mediators

See Table 3.11

Table 3.15 - Summary of Leukocyte Numbers per visit (D-8, D5)

See Table 3.09

Table 3.16 - Summary of Change from Baseline (D-8) to Infection (D5) for Leukocyte Numbers

See Table 3.09

Table 3.17 - Statistical Testing of Leukocyte Numbers

See Table 3.11

Table 3.18 - Summary of Blood and Sputum Eosinophilia

See Table 3.09

Table 3.19 - Summary of Change from Baseline to Peak Value for Blood and Sputum Eosinophilia

See Table 3.09

Table 3.20 - Statistical Testing for Blood and Sputum Eosinophilia

[figure not shown]
See Table 3.11

Secondary Analysis – Correlation Testing

Table 3.21 - Spearmans Rank Correlation Testing

Pearson Correlation Coefficients Prob > r under H0: Rho=0 Number of Observations		
	Var 1	Var 2
Var	XXXX	XXXX
XXXXXXXX.	XXXX	XXXX
	XX	XX
Var	XXXX	XXXX
XXXXXXXX.	XXXX	XXXX
	XX	XX

Figure 3.22 - Correlation Matrix

The above matrix can contain the following:

Baseline values of:

- ACQ (day 0)
- FeNO (day 0)
- Blood eosinophils (day -8)
- Serum IgE (day -8)
- PC₂₀ (day -9)
- Skin prick test (from screening)
 - # of allergens
 - Sum of wheal diameters (mm)
- Soluble mediators

Peak and AUC values of:

- Lower respiratory symptom score
- Upper respiratory symptom score
- Virus load
- Morning PEFR (peak decline)
- Morning FEV₁ (peak decline)
- Soluble mediators

vs

Secondary Safety Analysis

Table 3.23 - Summary of Adverse Events by Treatment and Timepoint

		Events			Patients		
		OC459	Placebo	Total	OC459	Placebo	Total
Timepoint	Total Number of AEs						
	Pre-Treatment (Wk1)						
	Pre-Inoculation (Wk2)						
	Assessment Phase (Wk3-4)						
	Follow-Up (Wk5-9)						

Table 3.24 - Summary of Adverse Events by Treatment and Severity

		Events			Patients		
		OC459	Placebo	Total	OC459	Placebo	Total
Severity	Number of Adverse events						
	Mild						
	Moderate						
	Severe						
Reason for SAE	Number of SAEs						
	Death						
	Life threatening						
	...						
	Other medical important events						
	Total						

Table 3.25 - Summary of Adverse Events by Treatment and Relationship to Study Treatment

	All Events						
Treatment	None	Unlikely	Possible	Probable	Definitely	Not Yet Defined	Total
OC459							
Placebo							
All subjects							
	Patients with AEs*						
Treatment	None	Unlikely	Possible	Probable	Definitely	Not Yet Defined	Total
OC459							
Placebo							
All subjects							

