4.4. Sample Size

An overall population size of 44 asthmatic subjects was based on the following assumptions:

- Type I error probability $\alpha = 5\%$
- Effect size = $(\mu_1 - \mu_0) / \sigma$
 - μ_i = mean PEP in group i ($i=1$: OC459, $i=0$: placebo),
 - σ = standard deviation of PEP
- PEP is primary end-point (=total daily lower respiratory symptom scores over D0 to D14, potential maximum of 315).

Based on a previously completed trial with similar design conducted at the same study site [10], σ is estimated to be 21.15 and the effect size equal to 22.21, yielding $n=15$ evaluable subjects per treatment group at 80% power. This is grossed-up for 80% rhinovirus inoculation success and adjusted for expected drop-outs to yield 22 enrolled patients per treatment group.

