7.2. Primary Analysis

Uncorrected lower respiratory symptom scores collected from D0 to D14 will be aggregated to create an overall total for each patient. Where patient scores are missing, data will be imputed based upon rules set within Section 7.5. Patients missing $\geq 20\%$ of score data will be excluded from any additional per-protocol analyses.

Data will be presented using summary statistics per treatment group and will include median and interquartile range (IQR). A supplementary plot showing individual measurements for both groups with a box & whisker overlay showing median and IQR will be produced.

Primary analysis to test for difference between the mean aggregated scores of the two treatment groups will be carried out using Mann-Whitney U tests. Differences will be considered significant at $P < 0.05$. All P values are two-sided.

An additional secondary analysis will take place correcting the scores for bronchoscopy-related symptoms. Full methodology will be clarified within Section 7.3.1 below.

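### The shell for the primary result table is titled Mann-Whitney but laid out with median-test scores, and several between-group tables reuse it

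*SAP*

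**What the plan says.** SAP section 7.2 sets the primary method: "Primary analysis to test for difference between the mean aggregated scores of the two treatment groups will be carried out using Mann-Whitney U tests". It adds "All P values are two-sided" and a 0.05 threshold. The Appendix A index and the shell in Appendix B carry the same title, "Table 2.03 – Mann-Whitney U Test of Total Lower Respiratory System Scores".

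The body of that shell is headed "Median Scores (Number of Points Above Median) for Variable Response Classified by Variable Treatment". Below it are columns for N, sum of scores, expected value, standard deviation under the null and mean score. A note reads "Average scores were used for ties". The shell then lists one- and two-sided p-values from a normal approximation, a t approximation and an exact test.

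Other Appendix B shells point back to it:
- Directly: Tables 3.02 and 3.04.
- Directly, for non-parametric variables: Tables 3.06, 3.08 and 3.11.
- Indirectly, through 3.11: Tables 3.14, 3.17 and 3.20.

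Separately, section 7.3.3 and the title of Table 3.21 call for Spearman rank correlations, but that shell is headed "Pearson Correlation Coefficients".

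**The concern.** A Mann-Whitney test sums ranks. A median test sums zeros and ones according to whether each subject lies above the pooled median, and discards everything else about the ordering. Both can be set out in the same columns, so a reader of the finished table could not tell from its layout that the test had changed.

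Shells exist to be programmed from, and the SAP gives no rule on whether text or shell prevails. If the programmer follows the shell, the primary p-value and the dependent between-group p-values come from a test that no section specifies. If both tests are run, the SAP offers written support for reporting either one, which pre-specification is meant to prevent.

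**Working it through.** **Inputs.** From SAP section 4.4: SD 21.15, difference 22.21, alpha 5%, power 80%, 15 evaluable per group. From section 7.2: two-sided testing at 0.05. Section 4.4 calls 22.21 an effect size in SD units. I read it as a raw difference in points, because 22.21 SDs would need about 1 subject per group.

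**The plan's own figure.** n per group = 2(1.960 + 0.842)² × (21.15/22.21)² = 15.70 × 0.907 = 14.2, rounded up to 15. The stated figure reproduces. The standardised difference is 22.21/21.15 = 1.05.

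**Rejection rule of the median test at 15 v 15, no ties.** Let S be the number in one arm above the pooled median. Under the null, S is hypergeometric (15 drawn from 30, of which 15 are above), with mean 7.5 and SD √[(15×15)/(30×29) × 30×0.25] = 1.393.
- S ≥ 11 or ≤ 4: exact p = 0.027; z = 3.5/1.393 = 2.51. Reject.
- S = 10 or 5: exact p = 0.143; z = 2.5/1.393 = 1.80. Do not reject.

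The test therefore works at an actual level of 2.7%, against about 4.5% for the exact Mann-Whitney test. That accounts for part of its lower power.

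**Power at 15 per arm.** Simulation, 40,000 trials per row, continuous data, exact two-sided Mann-Whitney, same difference and SD throughout. The shapes other than normal, and the gamma placebo means, are my assumptions; the documents give none. Losses are taken before rounding.

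| Shape | Mann-Whitney | Median test | Loss (points) |
|---|---|---|---|
| Normal | 76.2% | 52.4% | 23.8 |
| Gamma, placebo mean 35 | 95.1% | 84.4% | 10.7 |
| Gamma, placebo mean 45 | 87.3% | 68.6% | 18.7 |
| Gamma, placebo mean 60 | 81.3% | 59.7% | 21.7 |
| Gamma, placebo mean 80 | 78.3% | 55.3% | 23.0 |
| Laplace | 85.6% | 77.8% | 7.7 |

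With normal data rounded to whole scores and floored at zero (placebo mean 45 assumed), ties arise. Mann-Whitney keeps 76–77%; the median test has 49% in its exact form and 55% by normal approximation.

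**How often the two tests disagree.** In the normal case, Mann-Whitney alone was significant in 24.6% of trials and the median test alone in 0.9%. They gave opposite verdicts in 24.6 + 0.9 = 25.5%.

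**Which two-sided p-value.** For Mann-Whitney with normal data, the exact and normal-approximation p-values (continuity-corrected) each gave 76.2% power and the t approximation 73.0%. The three did not all fall on the same side of 0.05 in 3.2% of trials.

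**The case against.** The strongest reply is that the planned test is not in doubt. Section 7.2 names Mann-Whitney for the primary endpoint, sections 7.3.1, 7.3.2 and 7.4.1 name it again for other comparisons, and the index and table titles agree. No section mentions a median test. Against all this stands one heading in an empty shell, in an appendix with other signs of pasted templates: vital signs are headed as laboratory tests, Tables 3.30 and 3.31 cite a section 6.3.4 that does not exist, and the arm labels vary. This stands. It makes the point an appendix inconsistency rather than a choice of analysis, and harm follows only if output is built to the shell.

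Four stronger readings are tempting, and the documents do not support them:
- *The primary analysis is a median test.* The text and titles say otherwise.
- *Every non-parametric secondary result is affected.* The shell serves between-group comparisons only. Within-subject signed-rank tests and Spearman correlations do not use it.
- *A one-sided p-value could decide the trial.* Section 7.2 excludes that. Only the choice among exact, normal and t remains open, and it matters in few trials.
- *About a quarter of the power is lost whatever the data.* The loss is about 24 points for normal data but as little as 8 for the Laplace shape.

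**Conclusion.** The contradiction is real and is contained in a single table: the title and section 7.2 specify rank sums, while the shell displays counts above the median. Conditional on programming to the shell, power at 15 per arm would be about 52% instead of 76% under normality, with a loss of about 8 to 23 points under the other continuous shapes tried. The median test was weaker in every case. These figures rest on reading 22.21 as a raw difference, equal SDs and equal arms of 15.

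The sample size is unaffected. The planned method stands as written in section 7.2, so this should be fixed but does not call the design into question. The Pearson heading in Table 3.21 is a separate slip of the same kind and has no bearing on the primary analysis.

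**What to change.** 1. In Table 2.03, replace the heading and scores with Wilcoxon rank-sum scores. The existing columns can stay.
2. Carry the change to Tables 3.02 and 3.04, the non-parametric branches of 3.06, 3.08 and 3.11, and 3.14, 3.17 and 3.20.
3. State before unblinding which two-sided p-value is primary. The exact one is a reasonable example; naming one matters more than which.
4. Change the heading of Table 3.21 to Spearman coefficients, to match section 7.3.3.

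The cost is an edit to the SAP appendix and one sentence on the deciding p-value. Conduct, data collection and sample size do not change.
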